Steps to Eliminate Postoperative Problems

v1.3 6/26/2016

PRINCIPAL INVESTIGATOR: [name] [name], MSCE (Co-PI), [name], MPH (Co-PI)

PROTOCOL TITLE: Steps to Eliminate Postoperative Problems

NCT02880176

INTRODUCTION AND PURPOSE:

Radical cystectomy with urinary diversion is associated with substantial perioperative morbidity, including deep venous thrombosis, prolonged ileus, and postoperative functional decline. Post-operative morbidity after cystectomy prolongs the length of stay, increases the risk of readmission, and adds substantially to health care costs. Protocols that emphasize early and frequent ambulation after surgery decrease post-operative morbidity, but poor patient adherence diminishes the effectiveness of these protocols, which are currently implemented only during the hospital stay. Financial incentives overcome present bias and offer a novel and practical approach to increasing ambulation during the post-operative period in the hospital and after discharge. In this application, we propose a pilot randomized, controlled trial to estimate the effect size of financial incentives on increasing post-operative ambulation in the hospital and post-discharge after radical cystectomy. Secondary outcomes include step count, composite morbidity, and functional decline. This proposal will provide the preliminary data needed to design future, larger trials that will test the effect of financial incentives to increase ambulation on post-operative complications, readmissions, and functional decline

OBJECTIVES:

In this study, we seek to determine whether financial incentives can be used as novel and practical approach to increase post-operative ambulation and thereby decrease post-operative morbidity. The primary outcome variable will be the percentage of the first 30 post-operative days on which study participants meet patient-specific ambulation goals. Secondary outcomes include 1) the number of steps taken per day, 2) composite morbidity outcome of complications, unplanned readmissions, or Emergency Department (ED) visits, and 3) functional decline as measured by the Stanford Health Assessment Questionnaire.

BACKGROUND:

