Investigators, statisticians, and clinical staff will be blinded to participant group assignments. The research coordinator, however, will be unblinded by necessity. Participants similarly must be unblinded to their incentive structure, however they will not be told the incentive structure of the other group, nor whether their group is designated the treatment or control group.

Implementation of this project will occur in four phases.

- Phase 1: Preparation. (Study Approval – July 2016). During this phase, a research coordinator will be hired, equipment will be purchased, and all systems will be tested to ensure basic functionality prior to recruitment of the first participant.
- Phase 2: Recruitment. (July 2016 – June 2017). This phase describes the up to 10 month recruitment period during which patients will be screened and enrolled on a rolling basis into the trial.
- Phase 3: Data acquisition. (Enrollment – 30 days post-operative). This phase, which will overlap with phase 2 and start at a different time for each participant, describes the period for each participant in which they are enrolled and actively encouraged to submit data via the Way to Health platform and via interviews by the research coordinator. This phase bounds the total time commitment for any single study participant.
- Phase 4: Optional additional data submission and final survey (31 days post-operative to 90 days post-operative). This phase describes a period where patients will be allowed to continue to access the Way to Health platform and submit data should they choose to do so. No financial rewards or active encouragement will take place during this time. A final survey will be administered at the conclusion of this 90 day period to capture mid-term outcomes and complications.
- Phase 5: Analysis and Publication (Enrollment completion – December 2017). Final analysis of all acquired data is projected to be complete and ready for submission for publication by the end of 2017.

METHODS:

1. Study Instruments:

- Beginning shortly before the planned surgery and continuing for 30 days after date of surgery, all participants will use Fitbit Zips to measure daily step counts. Patients will have the option of submitting up to 90 days of post-operative data. Post-operative ambulation has been repeatedly demonstrated to be beneficial to recovery by a number of different metrics, and the Zip device has been shown to be an accurate measure of step counts.^{4-10,31}

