Participants enrolled in the data-collection phase of the study will be required to upload step count data daily to the Way to Health Website. Upload rates will be monitored and participants who fail to upload data for 24 hours will be contacted via their preferred contact phone number listed in the electronic medical record. The research coordinator will attempt to reach the participant daily for 3 days by phone, email, and the MyPennMedicine secure messaging service. If there is no response, the participant will be considered to have declined further participation. A final attempt will be made to contact the participant for the study conclusion interview. Regardless of participation status at the study conclusion, a check for all earned funds will be mailed to the study participant at the conclusion of the 30 day trial period. If participants stop uploading data daily but it can be confirmed that they are continuing to use the Zip device, arrangements may be made to upload the data for the study period in batch within 10 days of the conclusion of the study and allocate financial rewards according to the data collected.

STUDY PROCEDURES:

1. Detailed Description:

Participants will be enrolled on a rolling basis as they are identified. The following describes the sequence of steps for each participant

1. A potential participant is scheduled for radical cystectomy by the clinical staff. The surgical case is entered into the University of Pennsylvania Health System's electronic medical record by a Division of Urology surgery scheduler.
2. The research coordinator, with the assistance of clinical staff, reviews the surgery schedule on a weekly basis to detect patients who have been scheduled for radical cystectomy. Clinical staff are asked to alert the research coordinator if a patient is scheduled for cystectomy with a short lead time prior to the procedure. When a new case is scheduled, the coordinator reviews the patient's chart for eligibility.

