3. If the patient is deemed eligible and has an upcoming PAT or stoma-marking appointment, the patient is met by the research coordinator after the appointment. Consent is obtained, preoperative questionnaires are administered (see schedule below), the patient is given the Fitbit device, the patient is registered with WTH, randomization occurs, and the patient is instructed on how to upload data. Data collection begins immediately and preoperative step counts are uploaded to the WTH website. Patients with ECOG performance status greater than or equal to 3 will be screened for by review of the medical record and by asking patients to select which of the first four statements in the performance status best describe them.
 - a. In the event that eligible patients are identified with no PAT or stoma-marking visit prior to surgery, the patient will be contacted by phone. Preliminary verbal consent will be obtained, questionnaires will be administered, the patient will be registered with WTH and randomized and the Fitbit device will be mailed to the patient's home. Consent is finalized in the preoperative holding area.
4. The research coordinator will monitor the data being uploaded to WTH and follow up as needed with the patient to ensure that he or she is able to begin tracking and uploading step counts.
5. Demographic information for the participant is abstracted from the medical record and recorded along with questionnaire and randomization arm in the study database.
6. On the morning of the first post-operative day, the research coordinator explains the financial reward scheme specific to the patient's randomization arm.
7. The initial \$25 compensation for participation will be written and sent upon submission of the patient's preoperative step data.
8. In the morning of each day of the hospitalization, the research coordinator assists the patient in uploading the previous day's step-count data to the Way to Health website. The website provides feedback and allocates financial rewards into a virtual wallet. During this time, the research coordinator will also assess for safety and burden on the patient as well as assisting the patient in making any preparations to transition data collection to the home setting.
9. On the day of discharge, the patient will be prompted to respond to a brief questionnaire addressing perceived barriers to ambulation in the hospital.

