10. After discharge, participants resume independently for uploading their daily step count data. The website continues to provide feedback with each upload and may be accessed *ad lib* should participants want to check their progress and rewards more frequently. Data collection continues through the 30th post-operative day.
11. On the 31st post-operative day, the WTH platform prompts the participant to fill out questionnaires according to the schedule below. On the business day following the 31st post-operative day, the research coordinator will also contact the patient to inquire about any hospitalizations, stays at skilled nursing facilities or rehab facilities, emergency room visits, or unplanned doctor visits occurred since discharge and relevant medical records will be obtained if these are not already available through the UPHS EMR. Contact information is updated as needed, and financial awards are mailed in the form of a bank check to the participant's preferred mailing address. The research coordinator will follow up with patients to ensure the questionnaires are completed.
12. Participants are allowed to continue collecting and uploading data through WTH for 90 days post-operatively, although no further financial incentives or monitoring by the research coordinator will be provided.
13. On the 91st post-operative day, the patient is prompted to fill out questionnaires according to the schedule below. This will include a brief section addressing continued personal use of the Fitbit or another personal activity tracking device. On the business day following the 90th post-operative day, the research coordinator contacts the participant by phone to screen for uncaptured complications.

The schedule for questionnaires will be as follows:

- Initial contact (PAT visit, stoma-marking visit, or phone): SHAQ20, IPAQ, MPPSS
- Day of discharge: barriers to ambulation in the hospital
- 30 day post-operative phone call: SHAQ20, IPAQ, MPPSS, screen for uncaptured complications
- 90 day post-operative phone call: SHAQ20, IPAQ, MPPSS, screen for uncaptured complications

2. Data Collection:

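### Recovery of days worn but not uploaded is discretionary and runs through an unblinded coordinator, so ascertainment of the primary outcome could differ by arm

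*Combined protocol and SAP*

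**What the plan says.** OBJECTIVES defines the endpoint: "The primary outcome variable will be the percentage of the first 30 post-operative days on which study participants meet patient-specific ambulation goals". Neither that section nor STUDY PROCEDURES, 5. Statistical Analysis says how a day without data is scored.

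The route by which data arrive changes at discharge. In hospital, each morning "the research coordinator assists the patient in uploading the previous" day's counts (STUDY PROCEDURES, 1. Detailed Description, step 8), in both arms. From then on the participant does it: "After discharge, participants resume independently for uploading their daily step count data" (step 10).

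METHODS, 6. Subject Follow-up deals with lapses. After 24 hours without an upload, contact begins: "The research coordinator will attempt to reach the participant daily for 3 days by phone, email, and the MyPennMedicine secure messaging service". Then: "If there is no response, the participant will be considered to have declined further participation". One last contact attempt is planned, for the concluding interview. If continued device use can be confirmed, "arrangements may be made to upload the data for the study period in batch within 10 days of the conclusion of the study and allocate" rewards on the data obtained. No criteria are given for when this is done, who confirms use, or on what evidence.

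On blinding, STUDY DESIGN says: "The research coordinator, however, will be unblinded by necessity". The daily payment and the lottery exist only in the incentive arm (STUDY DESIGN). RISK/BENEFIT ASSESSMENT, 6. Compensation pays $75 in either arm for completing the study with at least 27 recorded days. Step 11 schedules a coordinator contact just after day 31 for health-care use and payment, and does not mention a device sync.

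**The concern.** The endpoint is meant to measure walking. After discharge it also depends on whether days held on the device reach the study database. When they do not, recovery rests on an unspecified judgement, made through the one staff member who must know the allocation, under a provision that itself links retrieval to paying rewards. The participant's reason to cooperate is also partly arm-specific.

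If more goal-met days were retrieved in one arm than in the other, the estimated effect would shift without any difference in walking. This pilot exists to supply effect sizes for larger trials, so such a shift would pass into their planning. Primary data already recorded could also be lost in either arm. A rule for scoring missing days cannot bring those days back.

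**Working it through.** **1. Payment figures in the plan.** Daily payment $1.50 and lottery prize $100 with chance 1/5 (STUDY DESIGN); 27-day threshold and $145 maximum (6. Compensation).
- Maximum: 30 × $1.50 + $100 = $145, as stated.
- Threshold: 27/30 = 90%, as stated.
- Lottery eligibility: 75% of 30 = 22.5 goal-met days.

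**2. What recovery is worth to a participant.** Assume d days worn but not uploaded, a share g of them goal-met, and all other days recorded.

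| d | g | Recorded without recovery | $75 regained in either arm? | Extra daily reward, incentive arm only (d × g × $1.50) |
|---|---|---|---|---|
| 5 | 0.3 | 25 | yes | 1.5 × $1.50 = $2.25 |
| 10 | 0.5 | 20 | yes | 5 × $1.50 = $7.50 |
| 15 | 0.7 | 15 | yes | 10.5 × $1.50 = $15.75 |

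The lottery adds at most 1/5 × $100 = $20 in expectation. The $75 motive stops once 27 days are recorded or can no longer be reached. The $1.50 motive continues for every goal-met day.

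**3. Bias if recovery is wholly one-sided and unuploaded days count as not met.** Assume 23 per arm (half of the planned 46), k controls with d unrecovered days each, a share g goal-met, and every equivalent incentive-arm day recovered. Understatement of the control mean = k × d × g / (23 × 30).
- Central: 5 × 10 × 0.5 / 690 = 25/690 = 3.6 points.
- Low: 3 × 5 × 0.3 / 690 = 4.5/690 = 0.7 points.
- High: 7 × 15 × 0.7 / 690 = 73.5/690 = 10.7 points.

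**4. Same scoring, partial asymmetry.** With the same true goal rate p in both arms, spurious difference = p × (upload rate, incentive − upload rate, control). Assume 95% in the incentive arm and 90%, 85% or 75% in the control arm.
- p = 30%: 1.5, 3.0 or 6.0 points.
- p = 50%: 2.5, 5.0 or 10.0 points.
- p = 70%: 3.5, 7.0 or 14.0 points.

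**5. Only uploaded days analysed.** Observed rate = p·u1 / (p·u1 + (1 − p)·u0), where u1 and u0 are the upload rates on goal-met and goal-missed days.
- If u1 = u0, the observed rate equals p and the bias is zero.
- If goal-met days are uploaded more often (u1 = 95%, u0 = 85%), an arm's rate rises by 2.3 to 2.8 points for p from 30% to 70%. With u0 = 75% it rises by 4.7 to 5.9 points.

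The values of k, d, g and p and all upload rates are assumptions; the documents give none of them.

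**The case against.** The monitoring, the 24-hour trigger, the three days of contact and the batch provision are worded alike for all participants, and in-hospital uploads are assisted in both arms. That stands, and confines the exposure mainly to days after discharge.

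Three stronger readings are tempting, and the documents do not support them.

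- *Controls have no financial reason to recover days.* They do. In every case in step 2 of the working, the $75 shared by both arms exceeds the extra daily reward, and also exceeds that reward plus the lottery's expected $20. The asymmetry is partial.
- *Non-responders' days are discarded.* The text says only that they are taken to have declined further participation. It plans one more contact attempt, does not limit the batch provision to those reached within three days, and leaves the platform open to day 90 (step 12). What is missing is an explicit recovery step.
- *The payment timing is contradictory.* Step 11 says that "Contact information is updated as needed, and financial awards are mailed in the form of a bank check to the participant's preferred mailing address", but gives no mailing date. 6. Compensation allows 10 days after the 30-day period, which can be read together with the 10-day batch window.

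It is also fair to say that the trial is a pilot, not powered for a significant difference. With an assumed SD of 20 to 30 points and 23 per arm, the 95% half-width is 1.96 × SD × √(2/23) = 11.6 to 17.3 points, wider than the bias in step 3. Imprecision does not excuse an avoidable bias, but it keeps the point in proportion.

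**Conclusion.** The point holds in conditional form. Recovery of recorded but unuploaded days is discretionary, has no criteria, and runs through a person who knows the arm, with a payoff that is partly arm-specific. It could therefore differ by arm and bias the primary outcome.

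A reader might go further and conclude that the plan favours the incentive arm. The documents do not show this: nothing in them fixes the direction or size. The 0.7 to 10.7 points (3.6 in the central case) illustrate fully one-sided recovery with unuploaded days scored as not met, a rule the plan does not state. If only uploaded days are analysed and the lost days are typical of their arm, the bias is near zero. This is a cheap improvement worth making, not a flaw that undermines the trial.

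**What to change.** Replace the discretionary sentence in METHODS, 6. Subject Follow-up with one rule for both arms.

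- At the day-31 contact in step 11, or at the final contact attempt already planned, ask every randomised participant who has not expressly withdrawn to do one final voluntary device sync, whatever their earlier upload or contact status.
- Count all data for post-operative days 1 to 30 retrieved within the window toward the primary outcome, and record by arm which days were recovered this way.
- Mail the check after the sync and no later than the 10-day limit in 6. Compensation. Close the sync window early enough to meet that limit, including for participants who never sync.
- In CHARACTERISTICS OF THE STUDY POPULATION, 5. Early Withdrawal of Subjects, which lets a participant withdraw just by no longer submitting data, state that ceasing to upload does not by itself rule out this one request.

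The cost is protocol wording in these sections, a few minutes at an existing contact, and a slightly later check for some participants. Some older days may no longer be on the device, so recovery may be incomplete. A stated scoring rule for days without data is still needed as well.

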The target population is adults undergoing radical cystectomy (RC) at the Hospital of the University of Pennsylvania (HUP). 75-100 patients undergo RC at HUP each year. We anticipate recruiting and retaining 50% of eligible patients (n=46) over a one-year enrollment period. Each patient will be followed for 30 days post-operatively with the option for patients to continue submitting data for up to 90 days after their procedure. We anticipate initiating recruitment in July of 2016.

2. Key Inclusion Criteria:

1. Patient is at least 21 years old. – This excludes pediatric patients who would certainly not be representative of the general cystectomy population.
2. Patient is planned to undergo radical cystectomy at the Hospital of the University of Pennsylvania. – This is the population to which we have access for recruiting purposes.
3. Patient is ambulatory with baseline ECOG performance status less than or equal to 2. – This excludes patients for whom step counts would not be relevant or a good measure of daily activity.

3. Key Exclusion Criteria:

1. Patient is non-ambulatory or use of Fitbit to monitor activity is otherwise impossible or impractical. – See inclusion criterion #3 above.
2. Patient has a preoperative ECOG performance status of 3 or greater. – See inclusion criterion #3 above.
3. Patient knows *a priori* that he or she will be unwilling or unable to use a mobile device and online tool to upload activity data.
4. Patient is incapable of consenting for him or herself prior to surgery – Because participation in this trial involves ongoing effort on the part of the subject, we exclude patients who are incapable of consenting for themselves at baseline.
5. Patient is unable to collect step count data for at least 3 days preoperatively – Because step count goals are determined based on preoperative status, we exclude patients for whom we have insufficient preoperative step count data.

4. Subject Recruitment and Screening:

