Potential participants will be identified from digital review of the HUP operating room schedule based on current procedural terminology (CPT) codes 51590, 51595, 51596, 51597 or others that may be used to encode radical cystectomy. OR schedules will be reviewed for the coming two months by the research coordinator in conjunction with clinical staff. All patients scheduled for cystectomy will have their charts reviewed for eligibility. After being scheduled for cystectomy, patients are usually seen at a separate pre-admission testing (PAT) appointment and/or an appointment for stoma marking. Scheduled patients will be approached at the conclusion of one of these visits for recruitment by the study coordinator. For the small number of patients who have neither of these visits preoperatively, the study coordinator will initiate contact over the phone, consent will be obtained, the device will be mailed to the participant's home, Way to Health staff or the study coordinator will assist the patient in set up of the device, the consent documents will be signed in the preoperative holding area.

5. Early Withdrawal of Subjects:

Participants may choose to withdraw by simply ceasing to submit ambulation data. Participants will agree that all data submitted to the Way to Health (WTH) will be retained and may be used as part of the study. However participants may stop submitting new data at any time. If a participant fails to submit data for 24 hours while hospitalized, he or she will be approached in the hospital by the research coordinator who can help resolve technical problems, answer questions, and obtain ongoing consent or register the participant's withdrawal. If a patient fails to submit data for 24 hours between the time when they begin submitting data preoperatively and the end of the 30 day post-operative period, the research coordinator will contact the patient by phone and carry out the same process of troubleshooting or registering withdrawal.

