Subjects will be assigned to groups using simple balanced randomization. Upon enrollment in Way To Health, patients will be automatically randomized into "financial incentives" and "control" arms by an off-site computerized randomization system which is part of the WTH platform.

4. Administration of Surveys and/or Process:

Step count data will be recorded and uploaded independently by participants after initial instruction by the research coordinator. Before and after hospitalization, the research coordinator will ensure that patients are successfully uploading data and will be available to address issues that arise.

Questionnaires will be administered via the Way To Health platform. At the specified time points in the study (initial enrollment, immediately prior to discharge from the hospital, 30 days post-operative, and 90 days post-operative) the patient will be prompted to log in to the platform and fill out the questionnaire. Responses will be automatically recorded to the secure database.

Patients will also be contacted by phone at 30 days and 90 days by the research coordinator to screen for complications that would not be present in the University of Pennsylvania Health System (UPHS) electronic medical record (EMR).

5. Data Management:

Data will be collected principally through the Way to Health platform, which is a web-based platform designed by the University of Pennsylvania Center for Health Incentives and Behavioral Economics specifically for the purpose of testing behavioral interventions such as ours in an academic research setting. This platform has already been used in a number of similar IRB-approved randomized trials at the University of Pennsylvania.

All data not stored on WTH will be stored on hospital or university-owned computers or on encrypted storage drives. Data access will be granted only as needed to a small number of researchers who have completed the appropriate training as mandated by the University of Pennsylvania.

Upon completion of the study, data collection sites will be taken down and data stores disconnected from live webservers. Data will be stored on research computers for a period of 5 years, after it will be stored entirely on encrypted archival drives if no follow-up projects have been initiated.

6. Subject Follow-up:

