For patients who do not have a PAT or stoma-marking visit, the research coordinator will attempt to reach the patient via his or her preferred telephone number in the medical record. A medical interpreter will be used if such was deemed necessary during the patient's clinical visit. The research coordinator will identify him or herself as an employee of the University of Pennsylvania working with the Division of Urology on research to promote improved surgical outcomes in patients undergoing radical cystectomy. He or she will identify the purpose of the call, to gauge interest in participation in a clinical trial investigating the effect of financial rewards on promoting behaviors that improve post-operative recovery. It will be emphasized that participation is entirely voluntary and that declining enrollment will not have any other effects on the patient's clinical care. If the patient expresses interest, a brief overview of the project will be provided in laymen's terms. The patient will then be given the opportunity to ask questions or schedule another time for further discussion. Questionnaires will be administered over the phone and the Fitbit will be mailed to the patient's house with instructions to begin data recording and uploading. Informed consent documents will be signed in the preoperative holding area on the day of surgery. This process of preliminary phone consent is necessary in order to obtain preoperative ambulation data. Data will be discarded from any patient who agrees to participate over the phone but ultimately declines participation prior to signing the formal consent documents.

At the time of initial contact, all participants and potential participants will be given a secure email address and phone number that can be used to contact the research coordinator with any questions that might arise before, during, or after the study period.

All adult subjects will be competent to consent. Assessment of competency is made by the clinical team at the time of consent for surgery. Only adults who sign their own consent form for radical cystectomy will be considered competent to consent for this study.

2. Waiver of Informed Consent:

Not applicable. No waiver is being sought.

RESOURCES NECESSARY FOR HUMAN RESEARCH PROTECTION:

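### Randomization fires at platform registration, before the baseline that sets every goal and, by phone, before signed consent, so eligibility and consent are settled after allocation with concealment not assured

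*Combined protocol and SAP*

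**What the plan says.** **When randomization happens.** METHODS, 3 (Method for Assigning Subjects to Groups) ties it to registration with Way To Health (WTH): "Upon enrollment in Way To Health, patients will be automatically randomized into" the two arms. STUDY PROCEDURES, 1 (Detailed Description), step 3 gives the same order for the clinic route: "the patient is registered with WTH, randomization occurs, and the patient is instructed on how to upload data". Step collection follows. Step 3a does likewise for people recruited by phone, after preliminary verbal consent: "the patient will be registered with WTH and randomized and the Fitbit device will be mailed".

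**What is settled afterwards.** Under INFORMED CONSENT, 1 (Consent Process), phone recruits sign in the holding area on the day of surgery. For those who do not sign: "Data will be discarded from any patient who agrees to participate over the phone but ultimately declines participation prior to signing". Key Exclusion Criteria, item 5 reads: "Patient is unable to collect step count data for at least 3 days preoperatively". Its stated reason is that "we exclude patients for whom we have insufficient preoperative step count data".

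**Why the baseline matters.** OBJECTIVES defines the primary outcome as the percentage of the first 30 post-operative days on which a patient-specific goal is met. STUDY DESIGN sets each goal as 10%, 25%, 40% or 55% of the lead-in baseline, by period. No substitute goal is given.

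**Blinding and analysis.** STUDY DESIGN leaves the research coordinator unblinded. Steps 4 to 6 of the Detailed Description have the coordinator follow up lead-in uploads, put the arm in the study database, and explain the reward scheme on the morning of post-operative day 1. The Statistical Analysis section names no analysis set.

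**The concern.** Randomization protects a comparison only if the people compared are those randomized, and if nobody who knows the arm can influence who stays in. Here the last two entry conditions, a signed form (phone route) and a usable baseline, are settled after the arm has been generated. The same coordinator who is described as unblinded pursues the lead-in data and handles consent.

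At stake is the pilot's main product, an effect size for planning larger trials. If some randomized people are removed and the analysis set is not named, a reader cannot tell which population the estimate describes or whether the removals were even-handed.

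**Working it through.** **1. Order of events**

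| Event | Clinic route | Phone route |
|---|---|---|
| Consent | Obtained at the visit | Verbal first; signed on the day of surgery |
| Randomization | Same visit, at WTH registration | At WTH registration, listed before the device is mailed |
| Lead-in step counts | After randomization | After randomization |
| Participant told the scheme | Post-operative day 1 | Post-operative day 1 |

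No one has lead-in data when randomized. Phone recruits have verbal but not signed consent.

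**2. Two readings of exclusion 5**

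- *Data-obtained reading.* The rationale speaks of data that are insufficient. Such data exist only after randomization, so applying the criterion removes randomized people.
- *Screening reading.* Inability to collect 3 days could be judged from the surgery date. Step 2 supports this, since staff are asked to "alert the research coordinator if a patient is scheduled for cystectomy with a short lead time". But a surgery date shows only that 3 days are available, not that they were recorded. Someone randomized who then records too few is not excluded. With no recorded day there is nothing to take a percentage of. With 1 or 2 days the plan does not say whether a goal is set. The goal, and hence the primary outcome, is undefined.

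**3. Concealment**

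The coordinator is unblinded, but no time of unblinding is given. Step 5 records the arm before step 6 uses it. No sentence withholds it until then. Concealment is therefore not assured during the lead-in or, by phone, at signature.

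**4. The plan's own sample figure**

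The plan gives 46 as half of eligible patients, recruited and retained, from 75 to 100 cystectomies a year. Half of that volume is 0.5 × 75 = 37.5 to 0.5 × 100 = 50, so 46 lies inside the range. It is exact for 46 / 0.5 = 92 eligible patients, a number not stated. The figure is net of loss.

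**5. How large could arm-related exclusion be? (illustration only)**

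The documents give no loss rate, SD or success rate. Assumed: 23 per arm, 50% of days met in an arm, 5 exclusions split 3:2, and excluded people who would have met a share b = 20% or 35% of goals.

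Shift in an arm's mean when k of 23 are removed, with q = k/23: (0.5 − q·b)/(1 − q) − 0.5.

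- b = 0.20: k = 3 gives 4.50 points and k = 2 gives 2.86; net 1.64.
- b = 0.35: k = 3 gives 2.25 and k = 2 gives 1.43; net 0.82.

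Standard error of the arm difference = SD × √(2/23): 5.9, 8.8 and 11.8 points for SD = 20, 30 and 40.

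**6. What an unstated rule could do (hypothetical)**

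Nothing in the documents proposes scoring people without a goal as 0% of days met. If an analyst did so for k of 23 in each arm, a difference D would become D × (1 − k/23). For an assumed D of 20 points, k = 1, 2 and 5 give 19.1, 18.3 and 15.7. This shows only why the screening reading needs a stated rule.

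**The case against.** The strongest reply is that little harm follows. Participants hear their scheme only on post-operative day 1, after the lead-in and after signature, so their own decisions to drop out cannot depend on it. The phone route is rare by the protocol's account ("For the small number of patients who have neither of these visits preoperatively"). Uploads are made by participants, and the rule on contact after 24 hours without data covers both arms. The handling is also partly stated: non-signers are discarded and exclusion 5 addresses a short baseline. All of this stands, and it keeps the likely bias small. It does not supply a hold on the arm, a reading of exclusion 5 or an analysis set.

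A reader might infer that early randomization also costs precision, and that later randomization would recover it. The documents do not support this. A person without a signature or a baseline is unusable under either timing; moving the trigger turns a post-randomization exclusion into a screen failure. The 46 is already stated as retained.

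A reader might also infer that the unblinded coordinator biases who remains. That is possible, but nothing in the documents shows it.

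**Conclusion.** The point holds as a matter of sequence and concealment. The order of events is explicit, and so is the absence of an analysis set. That data are discarded for non-signers after randomization is also explicit. Removal under exclusion 5 depends on its reading and is less certain; on the other reading the gap is an undefined primary outcome instead.

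Bias cannot be sized from the documents. Under the assumptions shown it is 0.8 to 1.6 points, well below the standard error. In a pilot that states it is not powered, this would not overturn a result. The change is still worth making because no stated step uses the arm before step 6 (step 5 only records it), so allocating early gains nothing. I treat it as a cheap improvement, not a flaw that undermines the trial.

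**What to change.** Keep registration, device and questionnaires at first contact. Trigger WTH randomization only once consent is signed and at least 3 lead-in days are recorded, at the latest just before step 6 on the morning of post-operative day 1. State that exclusion 5 is applied to data obtained, before randomization. State in the Statistical Analysis section that everyone randomized is analysed.

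*Cost.* Protocol wording, a change to the WTH trigger (the documents do not say how easy that is), and one added task on post-operative day 1 for a coordinator employed at 0.75 full time. No extra visit is needed, because steps 6 and 8 already bring the coordinator to the patient that morning.

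*If the trigger cannot move:*
- Withhold the arm from the coordinator until post-operative day 1.
- Apply exclusion 5 from a WTH count of recorded days only. The Subject Privacy section limits step counts to the patient, the coordinator and the website, so investigators should not see the counts themselves.
- Define the analysis set as all randomized people who signed consent and have a valid baseline.
- Report post-randomization exclusions by arm, with reasons.

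This fallback needs wording, the hold on disclosure and a day count from WTH.
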